15.2. General Information

The Investigator should refer to the current Investigator's Brochure along with subsequent Safety Alert Letters, the Clinical Study Operations Manual, Pharmacy Manual, Laboratory Manual, CRF Completion Guidelines, and all other study-specific information that is provided during the study initiation visit or by the study monitor.

15.3. Dissemination of Study Results

The information that is developed during the conduct of this clinical study is considered to be strictly confidential. This information may be disclosed only as deemed necessary by Sarepta Therapeutics Inc. However, at the conclusion of this clinical study, a clinical study report will be prepared. In addition, a manuscript will be prepared for publication in a reputable scientific journal under the direction of the Sponsor. Sarepta Therapeutics Inc., will publish and

[REDACTED]

communicate the clinical study results, irrespective of positive or negative findings. Data generated for this study will be exclusively owned by Sarepta Therapeutics Inc., as detailed in the Clinical Trial Agreement. The study will be registered on ClinicalTrials.gov. After completion of the study, results will be disseminated through ClinicalTrials.gov.

15.4. Product Handling and Complaints Reporting

If there are any issues during the course of the study related to the quality of the investigational product, the Investigator, clinical site pharmacist or pharmacy designee must contact the Sponsor or designated contract research organization (CRO).

## LIST OF ABBREVIATIONS AND DEFINITIONS OF TERMS

The following abbreviations, acronyms, and terms are used in this statistical analysis plan.

Abbreviation	Definition
AE	adverse event
AUC	area under the plasma concentration-curve
CL	total clearance
CL R	urinary clearance
C max	maximum plasma concentration
DMD	Duchenne muscular dystrophy
DSMB	Data Safety Monitoring Board
eCRF	electronic case report form
ECG	electrocardiogram
ECHO	echocardiogram/echocardiography
EOS	End-of-Study
IVR	Interactive Voice Response
IV	intravenous
LTE	long-term extension
MedDRA	Medical Dictionary for Regulatory Activities
CCI	
MRT	mean residence time
CCI	
PK	pharmacokinetics
CCI	
PT	preferred term
SAE	serious adverse event
SAP	statistical analysis plan
SMQ	standard MedDRA queries
SOC	system organ class
TEAE	treatment-emergent adverse event
t max	time of maximum plasma concentration
t 1/2	elimination half-life
V ss	apparent volume of distribution at steady state
WHO	World Health Organization
6MWT	6-minute walk test

## **2. INTRODUCTION**

The purpose of this statistical analysis plan (SAP) is to provide a detailed description of the statistical methods and procedures that will be used to analyze and report results for Study 4045-101, titled “A Randomized, Double-Blind, Placebo-Controlled, Dose-Titration, Safety, Tolerability, and Pharmacokinetics Study Followed by an Open-Label Safety and Efficacy Evaluation of SRP-4045 in Advanced Stage Patients with Duchenne Muscular Dystrophy Amenable to Exon 45 Skipping”.

This SAP has been prepared based on Protocol Amendment 3, dated 29 March 2018.

### **3. STUDY OBJECTIVES**

#### **3.1. Primary Objectives**

The primary objective of this study is to evaluate the safety and tolerability of 4 escalating intravenous (IV) doses (4, 10, 20, and 30 mg/kg) of SRP-4045 (casimersen) administered once weekly for at least 2 weeks per dose level compared with placebo.

#### **3.2. Secondary Objectives**

The secondary objective of this study is to determine the pharmacokinetic (PK) profile of 4 escalating IV dose levels of casimersen.

CCI

## 4. STUDY DESCRIPTION

### 4.1. Study Overview

This is a first-in-human, multicenter, randomized, double-blind, placebo-controlled, dose-titration study designed to assess the safety, tolerability, and PK of once-weekly IV infusions of casimersen in advance-stage patients with genotypically confirmed Duchenne muscular dystrophy (DMD) with an eligible deletion amenable to exon 45 skipping (eg, 12-44, 18-44, 44, 46-47, 46-48, 46-49, 46-51, 46-53, or 46-55).

Twelve patients will be randomized (2:1) in double-blind fashion to receive SRP-4045 (n=8) or placebo (n=4). Patients will receive a once-weekly IV infusion of SRP-4045 or placebo at escalating dose levels, each for at least 2 weeks: 4 mg/kg at Weeks 1-2; 10 mg/kg at Weeks 3-4; 20 mg/kg at Weeks 5-6; and 30 mg/kg beginning at Week 7. During the dose titration period of the study, dosing will be interrupted or halted if specific predefined stopping criteria are met, or if interruption is otherwise warranted at the discretion of the Sponsor or Investigator. Once the last patient has received 2 infusions at 30 mg/kg (Week 8), an independent Data Safety Monitoring Board (DSMB) will review cumulative safety data. Review by the DSMB is necessary for advising the Sponsor about whether the safety data allow for longer-term dosing with SRP-4045. Patients will continue to receive their randomized treatment (SRP-4045 or placebo) in a blinded fashion until the DSMB review is complete. Based on the results of this review, the Sponsor will determine whether to roll over the patients into the open-label extension period. During the open-label extension, patients will receive SRP-4045 at 30 mg/kg (or the highest tolerated dose as determined during the dose titration) administered weekly. All activities for these subjects will be outlined in a LTE study protocol.

CCI

[figure not shown]
[figure not shown]

Figure 1: Study Schematic

## **4.2. Sample Size and Power**

Sample size for this study is based upon qualitative considerations; no formal sample size calculations will be performed. The anticipated sample size is 12 total patients (8 casimersen and 4 placebo) in double-blind period and the same 12 patients will receive SRP-4045 in the open-label period). The selected sample size is considered sufficient to provide initial safety evaluation of SRP-4045 and to provide adequate data to allow for estimation of PK parameters.

## **4.3. Randomization and Blinding**

### **4.3.1. Randomization of Treatments**

After qualifying for study entry by confirming all eligibility criteria, DMD patients with an out-of-frame deletion mutation confirmed as amenable to exon 45 skipping will be randomized using a 2:1 ratio to either casimersen (8 patients) or placebo (4 patients). Randomization will be performed prior to dosing at Baseline/Week 1 using an Interactive Voice Response (IVR) system.

### **4.3.2. Blinding of Treatment**

This study includes a double-blind, placebo-controlled dose-titration period of at least 12 weeks during which all patients, parents, Investigators, and site staff not involved with drug product preparation will be blinded to treatment assignment. A double-blind, placebo-controlled study design will be used to reduce potential bias during data collection and evaluation of outcome parameters. Eight patients will receive weekly IV doses of SRP-4045, and 4 patients will receive weekly IV doses of placebo in a blinded fashion until approximately 4 weeks after the last enrolled patient received 12 weeks of treatment. Only individuals (ie, the qualified pharmacist and back-up pharmacists) who are authorized to verify dose and dose assignment will be unblinded to treatment assignment. These individuals will not interact with study participants and will be instructed not to divulge randomization assignment to others under any circumstances, unless directed to do so by the Investigator in the interest of patient safety.

During the open-label extension period, treatment assignment at the double-blind period will remain blinded until final database lock for the final data analysis.

## **4.4. Study Endpoints and Other Variables**

The study endpoints for which the statistical methods will be described in this SAP comprise all safety, PK, and efficacy endpoints.

#### 4.4.1. Safety Endpoints

The safety and tolerability of casimersen doses at 4, 10, 20, and 30 mg/kg for at least 2 weeks per dose for double-blind and open-label period will be assessed through a review and evaluation of the following:

- incidence of treatment-emergent adverse events (TEAEs)
- incidence of clinical laboratory abnormalities (hematology, chemistry, coagulation, urinalysis)
- incidence of abnormalities in vital signs and physical examinations
- incidence of abnormalities on electrocardiograms (ECGs) and echocardiograms/echocardiography (ECHOs)

[figure not shown]
#### 4.4.2. Pharmacokinetic Endpoints

The following PK parameters will be determined for both the double-blind and open-label periods:

- maximum plasma concentration ( $C_{max}$ )
- time to maximum plasma concentration ( $t_{max}$ )
- area under the plasma concentration-curve (AUC)
- apparent volume of distribution at steady state ( $V_{ss}$ )
- elimination half-life ( $t_{1/2}$ )
- total clearance (CL)
- mean residence time (MRT)
- urinary clearance ( $CL_R$ )

For the open-label extension period, CCI [REDACTED] will be explored. Serum PK parameters listed above will be determined for Week 60.

CCI

CCI

## 4.5. Planned Analyses

### 4.5.1. Periodic Safety Review

Periodic safety analyses were performed for safety reviews, the Investigator's Brochure update, and regulatory submissions (Development Safety Update Report). These periodic safety analyses were monitored by a Data Safety Monitoring Board (DSMB) and were reviewed approximately every 6 to 12 months during this study.

### 4.5.2. Final Analysis

A final analysis of safety, PK, and efficacy will be conducted once the last patient completes the entire study and the resulting database is cleaned, quality assured, locked, and unblinded. The study team will be unblinded to perform the final analysis. All statistical analyses will be performed by or under the supervision of the Sponsor.

All available data will be included in data listings and tabulations.

## 5. GENERAL STATISTICAL METHODS AND CONVENTIONS

### 5.1. General Methods

For continuous variables, descriptive statistics will include the number of patients with data to be summarized (n), mean, standard deviation (SD), median, minimum, and maximum.

For categorical/qualitative variables, descriptive statistics will include frequency counts and percentages. The total number of patients in a treatment group will be used as the denominator for percentage calculations, unless stated otherwise.

Unless stated otherwise, summaries of all endpoints will be by treatment group (see below for definitions of treatment groups) for 3 "Analysis Periods" (Double-Blind Period, Casimersen Period and Combined Double-Blind and Open-Label Periods):

Double-Blind Period: Data will include all assessments and events that occurred prior to the first dose of 30 mg/kg of casimersen in the open-label period. The analyses for the double-blind period will be primarily for safety.

Double-blind Period analysis treatment groups are:

- patients who received placebo during the double-blind Period
- patients who received casimersen at 4 mg/kg (Weeks 1-2), 10 mg/kg (Weeks 3-4), 20mg/kg (Weeks 5-6), and 30mg/kg (Weeks 7-8)
- <=20 mg/kg during Week 1 to 6 (only used for select endpoints)
- patients who received casimersen at 30 mg/kg during Weeks 7 to the end of the double-blind period
- patients who received casimersen at any dose level during Weeks 1 to the end of the double-blind period

Casimersen Period: For AEs and other safety-related data analysis, data will include all assessments and events that occurred while patients received casimersen. Assessments and events that occurred in the double-blind period for patients who were on placebo during the double-blind period will be excluded. Assessments and events that occurred during the double-blind period for patients who received casimersen will be included.

Casimersen Period Analysis treatment group is:

- all casimersen treated patients: Patients who receive casimersen in any portion of the study

Combined Double-blind and Open-label Periods: For efficacy data analysis, data will include all assessments and events during both treatment periods of the study.

Combined Double-blind and Open-label Periods Analysis treatment groups are:

- Placebo-Casimersen: Patients who receive placebo in the double-blind period followed by casimersen in the open-label period

- Casimersen-Casimersen: Patients who receive casimersen in both the double-blind and open-label periods
- Overall: All patients who are treated on the study with either placebo or casimersen

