### **6.8.1. Adverse Events**

In general, only TEAEs will be summarized. Nontreatment-emergent events will be recorded in the data listings. For all AE tables, the number and percentage of patients reporting AEs will be grouped using the MedDRA SOC and PT and summarized by Analysis period and, the treatment group as described in Section 5.1, and by dose level for the Double-Blind Period summary.

An overall summary table of TEAEs will be produced and will include the frequency and percentage of patients with TEAEs, treatment-related TEAEs, severe TEAEs, nonserious AEs, SAEs, treatment-related SAEs, AEs leading to discontinuation of study drug, the number of events at each severity level (mild, moderate, or severe).

Multiple occurrences of the same AE (at the preferred term level) in the same patient will be counted only once in the frequency tables. If a patient experiences multiple episodes of the same event with a different relationship/severity, the event with the strongest relationship or maximum severity to the study drug product will be used to summarize AEs by relationship and severity.

The following summary tables will be produced:

- TEAEs by SOC and PT
- TEAEs by SOC, PT, and severity
- TEAEs by descending frequency of PT
- treatment-related TEAEs by SOC and PT
- treatment-related TEAEs by SOC, PT, and severity
- treatment-related TEAEs by descending frequency of PT
- treatment-emergent nonserious AEs
- treatment-emergent SAEs
- treatment-related, treatment-emergent SAEs

The following listings will be produced:

- all AEs
- AEs leading to discontinuation
- all SAEs

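### SAP 5.1 sets one full-period placebo group beside casimersen dose groups with shorter windows, so crude AE percentages by dose are expected to read low against placebo even with no drug effect; any-dose versus placebo is unaffected

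*SAP*

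**What the plan says.** SAP 5.1 sets the double-blind data window without a week limit: "Data will include all assessments and events that occurred prior to the first dose of 30 mg/kg of casimersen in the open-label period". Within it there is one placebo group, "patients who received placebo during the double-blind Period". The casimersen groups are cut by week:

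- the titration steps, with all four doses sharing one bullet: "patients who received casimersen at 4 mg/kg (Weeks 1-2), 10 mg/kg (Weeks 3-4), 20mg/kg (Weeks 5-6), and 30mg/kg (Weeks 7-8"
- a pooled low-dose group, 20 mg/kg or less over the first six weeks, kept for certain endpoints
- a top-dose group running from Week 7 until double-blind treatment stops
- an any-dose group, which alone spans the same time as placebo: "patients who received casimersen at any dose level during Weeks 1 to the end of the double-blind period"

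Percentages are crude: "The total number of patients in a treatment group will be used as the denominator for percentage calculations, unless stated otherwise". SAP 6.8.1 summarises AEs by these groups "and by dose level for the Double-Blind Period summary" and counts each preferred term once per patient. SAP 6.8.2 (AEs of special interest) and SAP 6.8.3 (additional AEs for review) follow the same layout.

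SAP 5.8 derives patient years for casimersen overall, casimersen at 20 mg/kg or less, casimersen at 30 mg/kg, and placebo. SAP 6.7 presents only overall casimersen exposure for the double-blind period, not exposure by dose level. Neither document splits placebo by week or plans an exposure-adjusted AE rate.

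**The concern.** A patient counted once per term is more likely to be counted the longer he is observed. A placebo column covering 12 to 16 weeks or more, set beside a casimersen column covering 2, 6 or 10 weeks, will tend to show the higher percentage even if the drug does nothing. A reader going along the row by dose could take this as reassurance about the lower doses. The primary objective is safety at four dose levels compared with placebo, so these columns will be read, and the planned exposure tables show no patient-time by dose that would reveal the imbalance.

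**Working it through.** **Length of the period.** SAP 4.3.2 gives at least 12 weeks, with blinded treatment lasting until about 4 weeks after the last enrolled patient's 12 weeks: 12 + 4 = 16 for that patient, longer for earlier ones. Protocol 8.3 gives about 128 open-label weeks out of 144 for the last patient: 144 - 128 = 16. The two agree.

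**Time at risk.** Ratio of placebo window T to dose window t:

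- 20 mg/kg or less (6 weeks): 16/6 = 2.7; 12/6 = 2
- 30 mg/kg, Week 7 to end (T - 6 weeks): 16/10 = 1.6; 12/6 = 2
- second bullet read as one Weeks 1-8 group: 16/8 = 2; 12/8 = 1.5
- second bullet read as four 2-week columns: 16/2 = 8; 12/2 = 6
- any dose: 1

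**Direction.** Each dose window lies inside the placebo window. With no drug effect, expected placebo incidence is therefore at least that of every dose column, and higher whenever first events can fall outside that window. This needs no assumed rate. It does assume that an AE is assigned to a dose by its onset date, for which the SAP gives no rule.

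**Size.** The documents give no event rates, so these figures are illustrative. Assume a constant hazard, T = 16, and placebo incidence p of 25%, 50% or 75%. The expected percentage in t weeks at hazard ratio HR is 1 - (1 - p)^(HR x t/T). For example, at p = 50%, t = 6 and HR = 1: 1 - 0.5^(6/16) = 22.9%. The chances below are exact binomial for the observed percentages, with 8 casimersen and 4 placebo patients; the remainder are ties.

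No drug effect (HR = 1), at p = 25/50/75%:

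| Column | Expected % | Lower than placebo, % | Higher, % |
|---|---|---|---|
| 2-week step | 3.5/8.3/15.9 | 67/90/97 | 8/4/1 |
| 20 mg/kg or less | 10.2/22.9/40.5 | 60/76/84 | 20/13/8 |
| Weeks 1-8 as one group | 13.4/29.3/50.0 | 56/68/75 | 25/19/14 |
| 30 mg/kg, Week 7 to end | 16.5/35.2/58.0 | 51/61/66 | 30/25/20 |
| Any dose | 25/50/75 | 39/42/43 | 43/42/39 |

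Tripled hazard (HR = 3), chance of reading lower than placebo:

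| Column | Against full-period placebo, % | Against placebo for the same weeks, % |
|---|---|---|
| 2-week step | 60/76/84 | 11/14/11 |
| 20 mg/kg or less | 36/37/37 | 14/9/6 |
| 30 mg/kg, Week 7 to end | 20/17/15 | 11/7/6 |
| Any dose | 9/6/4 | 9/6/4 |

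At HR = 3 the any-dose column reads higher than placebo in 83/87/68%.

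**Sensitivity to onset pattern.** Put 80% of the cumulative hazard in Weeks 1-2, spread the rest evenly over the other seven 2-week blocks, and keep 50% placebo incidence. With H = -ln(0.5) = 0.693 and no drug effect, the 4 mg/kg step is expected at 1 - exp(-0.8 x 0.693) = 42.6%, and each later step at 1 - exp(-0.2 x 0.693/7) = 2.0%. The 4 mg/kg column then reads lower in 52% of cases, not 90%, while the gap at later steps widens.

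**Rare terms.** At 10% placebo incidence with no drug effect, a 2-week column reads lower in 34%, ties in 59% and reads higher in 7%.

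**The case against.** The strongest reply is that the comparison that matters is already planned. The primary endpoint (Protocol 7.3) concerns safety during the double-blind period with no split by dose, and Protocol 12.4.7 tabulates AEs by treatment group and overall. The any-dose group answers that, is time-matched to placebo and performs well under the same model. This stands. A reader might infer that the primary safety comparison is biased or that a real signal would be missed; the documents support neither.

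Second, 2-week columns are uncertain. The four doses share a bullet, SAP 6.3 itself calls 20 mg/kg or less and 30 mg/kg dose levels, SAP 5.8 derives no exposure for 4, 10 or 20 mg/kg singly, and four columns would give two overlapping 30 mg/kg groups. On the other side, SAP 6.7 makes an exception for individual dose levels and SAP 6.3 restricts one table to the pooled levels, which suggests single-dose columns elsewhere. A reader might take the 6-to-8-fold ratio as the plan's settled layout; the text does not settle it.

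Third, the tables are descriptive (Protocol 12.4.7), all AEs are listed (SAP 6.8.1), Study Day appears in listings as appropriate (SAP 5.9), and with 12 patients matched counts can be tallied by hand. That stands and limits the harm, though a safety table should not need reconstruction to be read correctly.

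Fourth, matching weeks does not isolate dose, because forced titration ties dose to time and prior exposure. That also stands and belongs in a footnote.

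**Conclusion.** The concern holds as a display bias in the by-dose AE tables. With no drug effect, every dose column is expected to read no higher than placebo, and usually lower. Two parts do not depend on event rates: this direction, and the time ratios (1.6 to 2.7 for the pooled columns at 16 weeks; 6 to 8 or more for 2-week columns, if shown). The percentages rest on assumed incidences and a constant hazard. With early-onset events the gap is small at 4 mg/kg and large at later steps, and rare terms mostly tie. For the pooled columns the effect is modest: with a tripled hazard they read lower than placebo in fewer than half of cases.

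No test or decision rule uses these columns, and the any-dose comparison is sound. The point is minor, or at most at the low end of what should be fixed before the tables are programmed.

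**What to change.** In SAP 5.1, name any-dose casimersen versus full-period placebo as the main double-blind comparison. For the 20 mg/kg or less and 30 mg/kg columns, and for any single-dose columns shown, add placebo for the same weeks and label these pairs descriptive. In SAP 6.7, show patient-time for every column used in the AE tables. Add a footnote that the windows are unequal and that dose is confounded with time under forced titration.

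The cost is SAP wording and a few table columns, with no new data. SAP 5.8 already derives patient years for placebo, 20 mg/kg or less and 30 mg/kg; single-dose columns would need the same derivation.

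The downside is sparse cells. With 4 placebo patients, a 2-week window holds no event with probability (1 - p)^(4 x 2/16) = 87/71/50% at p = 25/50/75%. One event there would read as 1/(4 x 14/365.25) = 6.5 per patient-year, so rates for such windows would mislead. For rare terms the patient-time and the footnote are the practical gain, and they are the minimum if matched columns are judged too thin.
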